1.2 Study objectives and endpoints

The objectives and related endpoints presented in [Table 1-1](#) will be evaluated in subjects with body weight of 90 kg or higher at randomization and with moderate to severe chronic plaque-type psoriasis.

Table 1-1 Objective and related endpoints

Objectives	Endpoints
Primary	
To demonstrate the efficacy of secukinumab 300 mg every 2 weeks in comparison to secukinumab 300 mg every 4 weeks with respect to PASI 90 response at Week 16	PASI 90 response at Week 16

[figure not shown]
Secondary

To demonstrate the efficacy of secukinumab 300 mg every 2 weeks in comparison to secukinumab 300 mg every 4 weeks with respect to Investigator's Global Assessment (IGA) mod 2011 0 or 1 response at Week 16.

IGA mod 2011 response at Week 16

To investigate the clinical safety and tolerability of secukinumab 300 mg every 2 weeks in comparison to secukinumab 300 mg every 4 weeks

Vital signs, clinical laboratory variables, ECGs, Adverse Events.

2 Statistical methods

Novartis will be performing the analysis. Statistical software SAS version 9.4 or later will be used.

2.1 Data analysis general information

Summary statistics for continuous variables will include N, mean, standard deviation, minimum, lower quartile, median, upper quartile, maximum. Summary statistics for discrete variables will be presented in contingency tables and will include absolute and relative frequencies.

If not otherwise specified, p-values will be presented as one-sided for hypotheses testings and as two-sided for other analysis. The level of significance will be set to 2.5% (one-sided, family-wise type-I-error). 95% confidence intervals will be displayed but not be used for decision making; they will only be used for estimation and will therefore always be two-sided.

All listings will be presented by treatment sequence.

Footnotes on outputs will be kept to a minimum also for outputs not covered in [REDACTED].

Footnotes will generally be provided for

- abbreviations used in the output; abbreviations used on several outputs, e.g. for listings in [Appendix 16.2](#) can be presented on a separate page and do not have to be repeated as footnotes on each listing
- sorting order of categories, e.g. for sorting within MedDRA (Medical Dictionary for Regulatory Activities) hierarchy levels

- MedDRA version used for reporting of MedDRA coded data

Footnotes will generally NOT be given for

- units displayed on the output
- interpretation of results (e.g. “odds ratio larger 1 favors active treatment”)
- information that can be retrieved from the statistical section of the clinical study report (CSR) unless it is not identifiable from the output, e.g.
 - explanation of analysis model used unless results of more than one model are displayed on an output
 - derivations of variables (e.g. BMI will not be explained on a footnote)
- information that will be provided in the clinical study protocol and/or methods section of the CSR (e.g. baseline definition if this is specified in the statistical section of the CSR)

2.1.1 General definitions

2.1.2 Study treatment

Novartis will supply the investigational therapy as follows:

- Secukinumab 150 mg solution for sub-cutaneous injection in a 1 ml pre-filled syringe
- Placebo solution for sub-cutaneous injection in a 1 ml pre-filled syringe

2.1.3 Study Day 1 and other study days

The first day of administration of randomized study treatment (first dose) is defined as *Study Day 1* or *Day 1*.

All other study days will be labeled relative to Day 1. For event dates on or after Day 1, study day for a particular event date is calculated as [Date of event] – [Date of first dose]+1, i.e., Day 2, Day 3, etc., will be one day, two days, etc., after Day 1, respectively. For the dates before Day 1, study day for an event date is calculated as [Date of event] – [Date of first dose], i.e., Day -1, Day -2, etc., will be one day, two days, etc., before Day 1, respectively. Duration of an event will be calculated as (Event end date – Event start date + 1).

The descriptor “Day 0” will not be used.

2.1.4 Screening, baseline and post-baseline definitions

Screening refers to any procedures (e.g., checking inclusion and exclusion criteria) performed prior to the date of first dose of study treatment (for safety analysis) or prior to the randomization date (for efficacy analysis). Per protocol, subject informed consent must be obtained prior to performing any study related activity. The date of signing informed consent is the start date of screening period. Any assessment obtained during the screening period will be labeled screening assessment. Assessments made on Day 1 may occur before or after the randomization or the first dose.

For efficacy analyses, baseline is the last assessment (including unscheduled visits) obtained on or before the randomization day. All assessments obtained after randomization are considered as post-baseline unless otherwise specified.

For safety analyses, baseline is the last assessment (including unscheduled visits) obtained on or before the first dose day of study treatment. All assessments obtained after the first dose of study treatment are considered as post-baseline unless otherwise specified.

2.1.5 Day of last dose of randomized study treatment

The date of last dose will be collected via the CRF. The subject's exposure will be calculated considering the end of study period visit (including follow-up visits F4, F8) or last dose day +84 days whichever occurs earlier.

On-treatment is defined as assessments within last dose plus 84 days.

2.2 Analysis sets

The following analysis sets will be used for the data analysis. Rules of exclusion criteria of analysis is detailed in [Section 5.5](#)

Randomized set: The randomized set will be defined as all subjects who were randomized at baseline visit. Unless otherwise specified, subjects misrandomized subjects will be excluded from the randomized set.

Misrandomized subjects are subjects who are screen-failures, but have been randomized by the investigator before eligibility was finally assessed, however have not been treated.

If subjects were re-screened and successfully randomized, they will be included in the randomized set according to the treatment assigned in the last randomization.

Full analysis set (FAS): The FAS will be comprised of all subjects from the randomized set to whom study treatment has been assigned. Following the intent-to-treat principle, subjects will be analyzed according to the treatment assigned to at randomization.

Of note, subjects excluded from the randomized set will be excluded from the FAS.

Safety set: The safety set includes all subjects who took at least one dose of study treatment during the treatment period. Subjects will be analyzed according to treatment received.

The treatment received will be set to the treatment randomized. But if a subject has received the wrong treatment during the entire study, the treatment received will be set to this wrong treatment.

2.2.1 Subgroup of interest

No subgroup analysis is planned for this study.

2.3 Patient disposition, demographics and other baseline characteristics

2.3.1 Patient disposition

The number of subjects screened will be presented. In addition, the reasons for screen failures will be provided. The number and percentage of subjects in the randomized set who completed study periods, and who discontinued the study prematurely (including the reason for

discontinuation), will be presented by treatment period 1, treatment period 2, entire treatment period and entire study period for each treatment group and all subjects.

For each protocol deviation, the number and percentage of subjects for whom the deviation applies will be tabulated. Additional listing for protocol deviations due to COVID 19 will be presented separately.

The patient disposition will be shown for below treatment groups:

The patient disposition will be shown for below treatment groups:

- for treatment period 1:
 - AIN457 300 mg Q2W
 - AIN457 300 mg Q4W
 - Total

A table with redacted content, likely showing patient disposition for treatment period 1. The table structure is obscured by black bars.

- Entire treatment period and Entire study period:

- AIN457 300mg Q2W
- AIN457 300mg Q4W (*in Randomization Process*) [AIN457 300 mg (eff)]

A table with redacted content, likely showing patient disposition for the entire treatment period and entire study period. The table structure is obscured by black bars.

- Total

2.3.2 Demographics and baseline characteristics

The following common background and demographic variables will be analyzed:

Continuous variables:

- Age
- Height
- Weight
- Body mass index (BMI)

Categorical variables:

- Age categories (<65 years, 65 years and older, 75 years and older)
- Gender
- Race
- Ethnicity
- Smoking status at baseline

Psoriasis specific baseline characteristics and history of disease will be summarized as well: baseline PASI, baseline PASI (≤ 20 , >20), baseline total BSA, baseline IGA mod 2011 score (at

least mild, moderate, severe), severity of psoriasis (CHMP guidelines, mild (total BSA <10% and PASI < 10), moderate ((PASI ≥10 or total BSA ≥10%) and PASI ≤20 and total BSA ≤20%), severe (total BSA >20% or PASI > 20)), psoriatic arthritis (yes, no), time since diagnosis of psoriasis, time since diagnosis of psoriatic arthritis, previous exposure to biologic systemic psoriasis therapy, previous exposure to systemic psoriasis therapy, previous exposure to non-biologic systemic psoriasis therapy, previous failure to biologic systemic psoriasis therapy, previous failure to systemic psoriasis therapy, previous failure to non-biologic systemic psoriasis therapy.

Body Mass Index (BMI) will be calculated using the following formula:

$$\text{BMI} = (\text{body weight in kilograms}) / (\text{height in meters})^2$$

For BMI, height and body weight the last value prior to randomization is used. If there is no weight recorded prior to taking of study treatment, BMI will be missing.

Of note: subject's height will not be remapped according to the analysis visit window.

Time since diagnosis of psoriasis (PsO) and time since diagnosis of psoriatic arthritis (PsA) will be calculated using the following formula:

$$\text{Time since diagnosis} = (\text{inform consent date} - \text{first diagnosis date} + 1) / 365.25$$

The first diagnosis date of PsO or PsA will be imputed according to the imputation rules in [Section 5.1.3.3](#)

Unless otherwise specified, summary statistics will be presented for continuous variables for each treatment group and for all subjects (total) in the randomized set. The number and percentage of subjects in each category will be presented for categorical variables for each treatment group and all subjects (total) in the randomized set.

Any condition entered on the *Relevant medical history / current medical conditions* CRF will be coded using the MedDRA dictionary. They will be summarized by System Organ Class (SOC) and Preferred Term (PT) of the MedDRA dictionary.

Summaries for cardiovascular medical history will be summarized by categories.

Smoking history will be summarized by treatment group.

Treatment groups defined in [Section 2.3.1](#) will be used as appropriate.

2.4 Treatments (study treatment, rescue medication, concomitant therapies, compliance)

2.4.1 Study treatment / compliance

The analysis of study treatment data will be based on the safety set.

The number of secukinumab and secukinumab placebo will be summarized by treatment group by means of contingency tables.

The duration of exposure to study treatment will be summarized by treatment group. In addition, the number of subjects with exposure of at least certain time thresholds will be displayed. The following categories will be presented: “any exposure”, “≥1 week”, “≥2 week”, “≥3 week” ,

“≥4 weeks”, “≥8 weeks”, “≥12 weeks”, “≥16 weeks”, “≥20 weeks”, “≥24 weeks”, “≥28 weeks”, “≥32 weeks”, “≥40 weeks” and “≥52 weeks”.

Duration of exposure will be defined as the time from first dose of study medication to the last dose plus 84 days or last visit (including follow-up visits) whichever occurs earlier. i.e., for subjects who discontinued or have their last visit earlier than 84 days, the end of study treatment exposure will be the date of the last study visit in the follow-up period or in the corresponding treatment period.

Duration of exposure (days) = min (‘end of treatment period’ date, last dose date +84) – first dose date +1

Duration of exposure (years) = duration of exposure (days) / 365.25s

Duration of exposure (100 subject years) = duration of exposure (years) / 100

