### **Treatment Period 2 (Week 16 post-dose to Week 52)**

Treatment Period 2 is the period from Week 16 through Week 52. The Week 16 dose is the first dose of the treatment Period 2 and the last dose will be administered at Week 48.

- Subjects from the 300 mg every 2 weeks group will remain on secukinumab 300 mg every 2 weeks until the end of treatment
- Subjects from the 300 mg every 4 weeks group:

- [REDACTED]
- [REDACTED]
- [REDACTED]

This allocation will be based on a pre-assignment done at the randomization/baseline visit.

The planned end of treatment period 2 visit (EOT 2) will be performed at Week 52.

For all subjects who discontinue study treatment prematurely for any reason before the end of treatment period 2/Week 52 (EOT2), an EOT2 visit should be performed approximately 4 weeks after their last dose of study drug and then subjects should enter the post treatment follow-up period.

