#### Home Administration

Between study visits, subject will be expected to perform home administration in order to have administration of study medication every 2 weeks. Home administration can be performed by subject or caregiver.

The following time points are planned for home administrations of study medication: Weeks 6, 10, 14, 18, 22, 26, 30, 34, 36, 38, 42, 44, 46 and 48.

At the randomization/baseline visit the subjects will be instructed by the site staff walking them through the "Instructions for Use" on how to self-inject via PFS. For subjects willing to self-inject, the first administration should be performed under guidance and supervision of a site staff member.

If the subject or caregiver is not able/confident to perform home administration, the subject will be allowed to return to the site for administration of the medication. However, during those visits no other assessments will be performed.

During home administration, subjects are expected to contact the investigator/site staff in case they are experiencing any AE/SAEs or have any concerns.

The investigator must promote compliance by instructing the subject to take the study treatment exactly as prescribed and by stating that compliance is necessary for the subject's safety and the validity of the study. The subject must also be instructed to contact the investigator if he/she is unable for any reason to take the study treatment as prescribed.

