- **Treatment period 1** (Randomization to Week 16 pre-dose including follow-up visits (F4 and F8) for patients prematurely discontinued during treatment period 1)
- **Treatment period 2** (Week 16 dose to EOT2/Week 52 including follow-up visits (F4 and F8) for patients prematurely discontinued)
- **Entire treatment period** (Randomization to EOT 2/Week 52 including follow-up visits (F4 and F8) for patients prematurely discontinued)
- **Entire study period** (Randomization to EOS/F8 including follow-up visits (F4 and F8) for all patients)

All data will be presented for the final analysis.

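### The exposure formula in SAP 2.4.1 stops at the end of the treatment period, while the SAP's own text runs to the last follow-up visit, so as printed a completer is credited 365 days instead of 421

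*SAP*

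**What the plan says.** The SAP gives the end of exposure three times.

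- SAP 2.1.5 calculates it "considering the end of study period visit (including follow-up visits F4, F8) or last dose day +84 days whichever occurs earlier".
- The sentence in SAP 2.4.1 runs from first dose "to the last dose plus 84 days or last visit (including follow-up visits) whichever occurs earlier".
- The formula in the same section reads "Duration of exposure (days) = min (‘end of treatment period’ date, last dose date +84", less the first dose date plus one.

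The first two agree. The formula puts a treatment-period date where they have the last visit.

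SAP 1.1 keeps these two ends apart. The entire treatment period is "Randomization to EOT 2/Week 52 including follow-up visits (F4 and F8) for patients prematurely discontinued". The entire study period is "Randomization to EOS/F8 including follow-up visits (F4 and F8) for all patients".

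For dosing, Protocol 3.1 (Treatment Period 2) says "the last dose will be administered at Week 48", and Protocol 5.5.4 lists home administrations at "Weeks 6, 10, 14, 18, 22, 26, 30, 34, 36, 38, 42, 44, 46 and 48". SAP 2.8.1 counts adverse events as treatment-emergent up to 84 days after the last dose for every subject. Protocol 9.5.2 promises exposure-adjusted incidence rates for selected adverse events.

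**The concern.** A programmer will normally code the formula rather than the sentence above it. Coded literally with the SAP 1.1 period definitions, it ends a completer's exposure at the Week 52 visit, although that subject is followed to F8 and the adverse-event window stays open until then.

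Protocol 3.2 records that the study was requested to evaluate both the treatment effect and the safety profile of higher exposure in heavier patients. Duration of exposure, the counts above each threshold and the subject-years are how the amount of safety observation will be described. If they follow the formula, they contradict the SAP's own definition, and a completer's events between Week 52 and F8 have no matching exposure time.

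**Working it through.** **Inputs.** First dose is Day 1, so Week w falls on Day 7w + 1. The last planned dose is at Week 48 (Protocol 3.1). SAP Table 2-1 schedules Week 52 on Day 365 and F8 on Day 421. A subject who stops early has EOT2 about 4 weeks and F8 about 12 weeks after the last dose (Protocol 3.1), taken here as 28 and 84 days.

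**Check of the plan's own figure.** Week 48 = 7 × 48 + 1 = Day 337, and 337 + 84 = Day 421. This is the scheduled F8 day, so for a completer the 84-day rule and the last visit coincide.

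**Completer on schedule.**

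- Text: min(421, 421) − 1 + 1 = 421 days.
- Formula with the treatment period ending at Week 52: min(365, 421) − 1 + 1 = 365 days.
- Difference: 421 − 365 = 56 days, and 56/421 = 13.3%.

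**Early stoppers who attend F8.** The result depends on what the formula's end date means. Exposure in days under each reading:

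| Last dose | Dose day | Text of 2.1.5 and 2.4.1 | Entire treatment period (SAP 1.1) | Own EOT2 visit | Day 365 for all | End of entire study period |
|---|---|---|---|---|---|---|
| Week 40 | 281 | 365 | 365 | 309 | 365 | 365 |
| Week 42 | 295 | 379 | 379 | 323 | 365 | 379 |
| Week 44 | 309 | 393 | 393 | 337 | 365 | 393 |
| Week 46 | 323 | 407 | 407 | 351 | 365 | 407 |
| Week 48 (completer) | 337 | 421 | 365 | 365 | 365 | 421 |

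Only the fourth column puts a stopper above the completer: by 14, 28 and 42 days for Weeks 42, 44 and 46, with a tie at Week 40. The completer still loses 56 days under the own-EOT2 and Day-365 readings. Only the last column agrees with the text.

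**Largest effect on a rate.** If events are counted to Day 421 but divided by 365 days, a completer's rate is inflated by 421/365 = 1.153, or about 15%.

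**The 52-week category.** At 7 days per week (an assumption, since the SAP states no conversion) the threshold is 52 × 7 = 364 days. A completer at 365 clears it by one day. An EOT2 visit two days early, on Day 363, would drop that subject from the category under the formula but not under the text.

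**The case against.** The best defence is that the formula is loose shorthand. Its term is in quotation marks and is not one of the labels defined in SAP 1.1. The sentence before it allows exposure to end at the last visit of the follow-up period or of the corresponding treatment period, so the term may stand for the end of whichever period is being reported. SAP 2.8 lists safety groups only for Treatment Period 1 and the entire study period; the entire treatment period appears for disposition (2.3.1) and the ECG abnormality count (2.8.5.2). If the reported period is the entire study period, a completer gets 421 days and nothing is lost. That may well be what was meant, but the SAP does not say so, and SAP 1.1 defines treatment period and study period as different things.

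The defence is right on several limits:

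- A reader might infer that the plan definitely credits early stoppers with more exposure than completers. It does so only if the term means the entire treatment period of SAP 1.1, and then only for subjects whose last dose was at Weeks 42 to 46 and who attended F8. The documents give no reason to expect many.
- A reader might infer that the reported adverse-event rates are 15% too high. The adverse-event analyses in SAP 2.8.1 and 2.8.2 are crude incidences with no person-time denominator. Only the exposure-adjusted rates in Protocol 9.5.2 could be affected. The 15% applies to a full completer; a pooled rate that includes discontinuers would move less.
- The same rule applies to completers in both arms, so the comparison of regimens would change little unless completion differs between them.
- The wide Week 52 window in SAP Table 2-1, opening at Day 324, maps assessments to visits. It is not evidence that EOT2 visits happen early.

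**Conclusion.** The conflict stands. The formula in SAP 2.4.1 does not match SAP 2.1.5 or the sentence above it. Taken as printed, with the SAP 1.1 treatment period, it gives an on-schedule completer 56 fewer days (13%) and stops short of the adverse-event window.

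What is directly affected is the set of exposure durations, threshold counts and subject-years. Any effect on exposure-adjusted rates is bounded at about 15%. The reversal between completers and Week 42 to 46 stoppers is conditional on one reading and should be reported that way. Efficacy and crude incidences do not use this quantity.

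The figures assume visits on schedule. If the sponsor meant the end of the reported period, the numbers already agree with the text and only the wording needs correcting. The point is worth settling before programming, because the intended rule cannot be read from the formula.

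**What to change.** For the entire study period, replace the formula for all subjects with: min(last study visit date including F4 and F8, last dose date + 84) − first dose date + 1. This is the rule already in SAP 2.1.5 and the 2.4.1 text. It gives 421 days for a completer and 379, 393 and 407 for last doses at Weeks 42, 44 and 46, so exposure again rises with the last dose.

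For Treatment Period 1, state that subjects who continue are capped at the Week 16 pre-dose date, in line with SAP 1.1. It would also help to state how weeks are converted to days for the threshold categories.

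The cost is a small edit to one SAP section and the matching line in the exposure program. It needs no new data and changes no clinical procedure.

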2.4.2 Visit window

Visit-windows will be used for the data that is summarized by visit; they are based on the study evaluation schedule and comprise a set of days around the nominal visit day. For any assessment, there are the protocol defined scheduled visits around which visit windows were created to cover the complete range of days within the study. The visit windows are shown in [Table 2-1](#). In this table, the days are counted since the first dose of study treatment (study days) for safety assessments, and the days are counted since the date of randomization for efficacy assessments. These visit windows apply to measurements taken at every visit. For assessments collected less often different visit windows will be applied as detailed below.

When visit windows are used, all visits will be re-aligned, i.e., they will be mapped into one of the visit windows. E.g., if the *Week 4* visit of a subject is delayed and occurs on Day 60 instead of on Day 29, it will be re-aligned to visit window *Week 8*. In the case of major deviations from the visit schedule, or due to unscheduled visits, several assessments of a subject may fall in a particular visit window (either scheduled or unscheduled). Statistical approaches to handle multiple assessments in a given visit window are specified below.

Table 2-1 Assessment windows for scheduled visits

Analysis Visit	Week	Scheduled Day	Visit Window
Baseline	BSL	1	-28 days to Day 1*
Week 1	1	8	Day 2-11
Week 2	2	15	Day 12-18
Week 3	3	22	Day 19-25
Week 4	4	29	Day 26-43
Week 8	8	57	Day 44-71
Week 12	12	85	Day 72-99
Week 16	16	113	Day 100-127

Week 20	20	141	Day 128-155
Week 24	24	169	Day 156-183
Week 28	28	197	Day 184-211
Week 32	32	225	Day 212-253
Week 40	40	281	Day 254-323
Week 52	52	365	Day 324-379
Week 56 (F4)	56	393	Day 380-407
Week 60 (F8)	60	421	Day 408-435

* Baseline measurement before the first drug administration for safety assessments and before the randomization for efficacy assessments.

For parameters which are not collected at every visit (e.g. weight, laboratory, [REDACTED]), visit windows defined in [Table 2-1](#) will be combined. For example, if a parameter is measured at Week 12 and Week 28 only, Week 12 visit window will extend from Day 2 to Day 99 (combining Week 1 to Week 12 visit windows), Week 28 will extend from Day 100 to Day 211 (combining Week 16 to Week 28). For safety parameters which are not collected after week 52 (e.g. ECG), upper limit will be extended to last day of study i.e. Day 435 and only ‘on-treatment’ events will be consider for analysis. If more than one assessment falls into the interval, the rules defined in [Section 2.4.3](#) below are applied.

The analysis visit will be used for listing of visit and period for both safety and efficacy data. If a visit falls after the last visit window (after Day 435) it is not assigned an analysis visit and will be listed under label “After Week 60”.

